- Prior to the visit, an unblinded member of the study team will randomize the participant to either the VLNC or NNC cigarette group based on a pre-determined block randomization list. The unblinded study member will identify the cigarette packs with the assigned nicotine content by NRC code and prepare them for redistribution by re-labeling each pack with the participant ID number and a label indicating these are research cigarettes. The unblinded study member will keep records of the RTI log numbers of the packs dispensed to each participant at each visit. At the end of MRI Visit 1 participants will be given an ample 6-week supply of their assigned cigarette (125% of baseline cigarettes per day) and instructed to only smoke study cigarettes until their next scheduled appointment. Participants may contact the study team to receive more study cigarettes if they run out prior to their next visit unless this is more than a 100% increase from their baseline CPD. Participants will be instructed to continue completing the daily REDCap cigarette log surveys that they receive via text message and will also be given paper cigarette logs to track use throughout the day.

Time commitment: 2 hours

7.2.3 Remote visit 1 (scheduled for +1 to +3 day(s) of in person MRI visit)

Participants will complete the following procedures over Zoom

1. REDCap Survey Questionnaire

- a. Depression (CESD)
- b. COPD (CCQ)
- c. Psychological Distress (Kessler K6)
- d. Nicotine Dependence
- e. Anxiety (ASQ)
- f. Sleep Disturbance
- g. Cigarette Liking
- h. Stages of Change
- i. Perceived Stress

2. Interview

- a. Concomitant medications
- b. Adverse event trigger questions

3. Out of scanner tasks

- a. Participants will complete a monetary temporal discounting task. During this computerized task, participants will choose between two options with specified dollar amounts and time delays to receipt of money (see MRI task image below).
- b. Participants will complete a computerized stroop interference task where they will view color words printed in the same color (i.e., blue, red, yellow, green), color words printed in an incongruent color (e.g., “blue” printed in red), and color neutral words printed in color (e.g., “hat” printed in red). Participants will be asked choose what color each word is printed in by pressing a button labeled to indicate each color.

7.2.4 Phone call 1

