7.2.5 Remote visit 2 (Week 3 ± 5 days)

Participants will complete a Zoom call three weeks into the randomization phase. During this visit participants will complete the following activities:

1. Review cigarette tracking logs with study staff.
2. Concomitant medication
3. Adverse event trigger questions
4. Discuss and problem-solve barriers to adherence
5. Computerized REDCap Survey Questionnaires (see Remote Visit 1 and MRI Visit 1)
6. Complete computerized out-of-scanner tasks.

Time commitment: 1 hours

Participants will be asked to refrain from smoking for 14 hours prior to MRI visit 2. The MRI visit 2 and Remote visit 3 will be scheduled.

7.2.6 Phone call 2

Participants will be contacted in the 4th week of the randomization phase to check-in regarding their next scheduled appointment and their success with cigarette tracking and study cigarette compliance.

Time commitment: 15 minutes

7.2.7 Remote visit 3 (scheduled for -1 to +1 day of in person MRI visit)

Participants will complete the following procedures over a Zoom call

1. Concomitant medications
2. Adverse event trigger questions
3. Perceived health risk rating
4. Computerized REDCap Survey Questionnaires (see Remote Visit 1)
5. Review cigarette tracking logs.
6. Complete computerized out-of-scanner tasks
7. Complete quit choice survey and counseling. Participants will be reminded that they will receive a text message survey in 12 weeks asking for information on quit attempts.

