7.4.6.3 Preparation and Dispensing

Assignment: When a new participant is randomized, they will receive the packs labeled with their study ID number indicating that these are research cigarettes.

Preparation: Once the cigarettes are received, they will be blinded by the unblinded study member. At the time of dispensation, the unblinded study member will prepare a bag of cigarette packs labeled with the participant ID number and indicating that they are research cigarettes. The RTI log number labels will be removed from the packs/cartons at the time of preparation for dispensing.

Where: All receiving, sorting, blinding of the initial study product will be done by an unblinded member of the study team in a designated space for this study at Penn State Hershey. Dispensing of product to study participants will occur at the Center for NMR Research where participants will complete their MRI visits.

Dispensing: Cigarette packs containing 20 cigarettes will be prepared by the unblinded study member prior to a participant's in person visit. All packs will be given to participants in the original packaging. Each individual pack of cigarettes will have a label with the participant ID number and a list of possible nicotine doses the cigarettes may contain. The coordinator will give the cigarettes to the participant at their second visit. The number of packs dispensed will be determined by the self-reported number of cigarettes per day they smoke determined by the baseline week cigarette log. Participants will be provided with 125% of the cigarettes necessary for each week of usual smoking. Participants will be able to smoke as many or as few cigarettes as they choose and will be required to return all packs (empty and full) at the next visit.

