- The scans done during this study are NOT designed to detect or evaluate any medical condition. They are intended solely for research purposes. The investigators for this project are not trained to perform medical diagnosis, and the scans to be performed in the study are not optimized to find abnormalities. On occasion, a member of the research team may notice a finding on a scan that seems abnormal. When a finding is noticed, one of the investigators may consult a physician specialist, such as a radiologist or neurologist, as to whether the finding merits further investigation. If the specialist recommends further follow-up, the investigator or another member of the research team will contact the participant within **48 hours** of the recommendation and suggest that the participant contact his or her private medical provider for follow-up. To facilitate follow-up care, the participant may be given a copy of the images upon written request. Being told about a finding may cause the participant anxiety as well as suggest the need for additional tests and financial costs. Medical insurance may be affected whether or not the finding is ultimately proved to be of clinical significance. Costs for clinical follow-up will not be covered in the cost of research. Participants will be told that their decision as to whether to proceed with further examination or treatment is their own.
- Increased compensatory smoking: Compensatory smoking may lead to increased levels of toxicant exposure. In prior studies, compensatory smoking was minimal and higher levels of toxicant exposure were generally not observed. Cigarette consumption will be monitored throughout the 6-week randomization phase. Safety rules are in place to identify and remove participants who increase their smoking rate significantly.
- Nicotine withdrawal symptoms: Decreased nicotine cigarettes and abstaining from nicotine may result in nicotine withdrawal symptoms (e.g. irritability, anxiety, restlessness, depressed mood, increased appetite, fatigue, insomnia/sleep problems, impatience, headache, difficulty concentrating, frustration, anger, craving for sweets, constipation, coughing, dizziness, nausea and sore throat).

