13.0 Sharing Results with Subjects

This study is not designed to diagnose any disease or condition. However, if during the course of conducting clinical procedures (e.g., MRI), a participant is found to have a result outside of clinical norms, the result will be discussed with the participant at the visit where the result is identified (MRI) or via phone after the visit. The participant will be given a letter indicating what procedure was done and will direct them to contact a medical provider for further evaluation. If a woman tests positive for pregnancy, the results will be shared with the participant and they will be advised to follow up with their doctor for prenatal medical care. They will not be allowed to participate in the study. Abnormal medical results, adverse changes in mental health status, increased toxicant exposure (CO and cigarette consumption) and other outcomes of the study will be treated as Adverse Events. They will be discussed with the participant, documented and the results will be reviewed by the study PI.

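### Depression, distress, anxiety, sleep, stress and COPD scales are first scored 1 to 3 days after the study cigarettes are dispensed, so no pre-exposure score exists for judging change

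*Combined protocol and SAP*

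**What the plan says.** Section 7.2.2 starts exposure on the day of the first scan: "At the end of MRI Visit 1 participants will be given an ample 6-week supply of their assigned cigarette", and participants are "instructed to only smoke study cigarettes until their next scheduled appointment". Section 7.4.6.3 agrees: "The coordinator will give the cigarettes to the participant at their second visit". With the final remote screen as the first visit, the second is MRI visit 1.

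Section 7.2.3 is headed "Remote visit 1 (scheduled for +1 to +3 day(s) of in person MRI visit". Its questionnaire list holds the CESD, CCQ, "Psychological Distress (Kessler K6"), ASQ, sleep disturbance and perceived stress. Section 7.2.5 (Week 3) and section 7.2.7 (Remote visit 3, around Week 6) repeat the Remote visit 1 questionnaires.

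The final remote screen (7.2.1), which is described as collecting baseline information, lists ten REDCap questionnaires and none of these six. MRI visit 1 (7.2.2) lists only the MNWS, the QSU and a craving questionnaire, after 14 hours without smoking.

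On safety, section 13.0 says that "adverse changes in mental health status, increased toxicant exposure (CO and cigarette consumption) and other outcomes of the study will be treated as Adverse Events". Section 11.0 says: "Decreased nicotine cigarettes and abstaining from nicotine may result in nicotine withdrawal symptoms (e.g. irritability, anxiety, restlessness, depressed mood", and goes on to include insomnia and sleep problems.

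**The concern.** An adverse change needs a reference value. For these scales the earliest value is taken when a VLNC participant may already have the symptoms that section 11.0 predicts, while an NNC participant has had no comparable fall in nicotine (0.29 mg against 11.6 mg, section 7.4.1).

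Two distortions follow when a later score is set against the first one. A worsening that begins on switching and persists looks smaller than it is, or absent. A worsening that begins on switching and then fades looks like improvement. Both favour VLNC. They matter most for the individual participant: staff cannot tell from the scales whether distress rose after the switch. They would also affect any later group analysis that uses the first score as its baseline.

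**Working it through.** **Schedule, with day 0 = dispensing at the end of MRI visit 1**

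| Contact | Timing | Six scales collected? |
|---|---|---|
| Final remote screen (7.2.1) | before day 0 | no |
| MRI visit 1, before dispensing (7.2.2) | day 0 | no |
| Remote visit 1 (7.2.3) | day +1 to +3 | first time |
| Remote visit 2 (7.2.5) | Week 3 | yes |
| Remote visit 3 (7.2.7) | around Week 6 | yes |

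The sign convention is clear, because the last remote visit is headed "Remote visit 3 (scheduled for -1 to +1 day of in person MRI visit": minus means before the scan and plus means after. Pre-exposure scores: 0 of 6 scales.

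**What is lost statistically.** The plan gives no power figure for these scales, so there is none to reproduce. Inputs: 50 VLNC and 25 NNC completers (7.1). Assumptions: outcome SD 1, correlation r = 0.5 between two scores, two-sided α = 0.05, and a VLNC effect d that persists to Week 6. Power comes from the noncentral t with 50 + 25 − 2 = 73 degrees of freedom and noncentrality d / (s × √(1/50 + 1/25)) = d / (0.245 s).

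1. Week 6 scores compared by arm, no baseline: s = 1. For d = 0.5 the noncentrality is 0.5/0.245 = 2.04 and power is 52%. For d = 0.3 it is 1.22 and power is 23%.
2. Week 6 scores adjusted for a pre-dispensing score: s = √(1 − r²) = √0.75 = 0.866. For d = 0.5 the noncentrality is 2.36 and power is 64%. For d = 0.3 it is 1.41 and power is 29%.
3. Change from a pre-dispensing score: s = √(2(1 − r)) = 1, so the power equals that in step 1.
4. Change from Remote visit 1, when a share a of the effect is already present there: the expected arm difference is d(1 − a), with s = 1.

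| a | Expected difference (d = 0.5) | Power |
|---|---|---|
| 3% | 0.485 | 50% |
| 14% | 0.430 | 41% |
| 43% | 0.285 | 21% |
| 100% | 0 | 5% |

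5. Week 6 scores adjusted for the Remote visit 1 score: the expected difference is d(1 − r·a). For d = 0.5 this is 0.465 at a = 14%, 0.393 at 43% and 0.25 at 100%. The bias is half that of the change score, in the same direction.

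**Where the shares come from.** The documents give neither the scales' recall windows nor the speed of onset. If the share absorbed equals the part of the recall window that falls after dispensing (days since dispensing ÷ window length), a 30-day window gives 1/30 to 3/30 = 3% to 10%, a 14-day window 7% to 21%, a 7-day window 14% to 43%, and a 1-day window 100%. These windows are illustrations, not facts about the instruments as used here.

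**The case against.** The strongest reply is that nothing planned depends on the missing score. Section 8.3 does not analyse these scales. Section 10.7 tests change from baseline for cigarette consumption only and keeps safety data pooled across arms unless the principal investigator asks for an unblinded look. No text calls Remote visit 1 the baseline for these scales. Randomisation also protects a comparison of Week 3 or Week 6 scores without any baseline. All of this stands.

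A reader might go further and infer that the trial could detect a lasting 0.5 SD worsening only 5% of the time, or would show a false improvement on VLNC in about half of trials if the worsening resolved. The documents do not support either. Both require an arm comparison of change from Remote visit 1, which is not planned, and full absorption by day 1 to 3, which is only the extreme case. For a resolving effect the false difference is a × 0.5 SD, which is significant in about 5% of trials at a = 3% and 14% at a = 43%; 52% is reached only at a = 100%.

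It can also be said that section 13.0 does not tie adverse-event decisions to these scales, that adverse event trigger questions are asked at every remote visit, that section 10.2 does not list the scales among reviewed safety data, and that some pre-exposure information exists: the exclusion for uncontrolled serious mental illness or suicidality, the medical history, and an MNWS before dispensing. This softens the point without removing it. The exclusion and the medical history are not scale scores. The MNWS is taken after 14 hours' abstinence, is not listed at Remote visit 1, and does not replace a depression or distress scale.

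**Conclusion.** The scheduling gap is certain and rests on no assumption: all six scales are first scored after dispensing. Its direction follows from section 11.0: change from the first score, or adjustment for it, tends to understate an early worsening on VLNC. Its size is unknown, because the share of any effect present at days 1 to 3 cannot be derived from the documents.

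The damage is limited to within-person judgement of change and to analyses that use the first score as a baseline. For arm comparisons, the gain from a true pre-exposure score is the step from 52% to 64% power for 0.5 SD, or 23% to 29% for 0.3 SD, under the stated assumptions. The primary endpoints in section 1.2 (reactivity to tobacco odor and smoking dependence) are not the subject of this point. It is a cheap improvement of minor severity, worth making early because a pre-exposure score cannot be recovered once cigarettes have been handed out.

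**What to change.** - In section 7.2.1, add the CESD, K6, ASQ, sleep disturbance, perceived stress and CCQ to the final remote screen, before any study cigarettes are given.
- Screening runs on verbal consent (section 5.2.2) and section 6.3 limits collection to essential information, so list the added scales and their purpose in the IRB submission.
- State that the screening score is the reference for mental-health change and for baseline adjustment in any arm comparison.
- Label the Remote visit 1 score as on-treatment, including for participants already enrolled, or drop that administration to offset the time. For those already past dispensing, rely on Week 3 and Week 6 comparisons without baseline.

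Cost: a small IRB amendment and an assumed 10 to 15 more minutes at an existing Zoom visit, offset if the Remote visit 1 copy is dropped. No new visit or staff is needed.

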7.2.5 Remote visit 2 (Week 3 ± 5 days)

Participants will complete a Zoom call three weeks into the randomization phase. During this visit participants will complete the following activities:

1. Review cigarette tracking logs with study staff.
2. Concomitant medication
3. Adverse event trigger questions
4. Discuss and problem-solve barriers to adherence
5. Computerized REDCap Survey Questionnaires (see Remote Visit 1 and MRI Visit 1)
6. Complete computerized out-of-scanner tasks.

Time commitment: 1 hours

Participants will be asked to refrain from smoking for 14 hours prior to MRI visit 2. The MRI visit 2 and Remote visit 3 will be scheduled.

7.2.6 Phone call 2

Participants will be contacted in the 4th week of the randomization phase to check-in regarding their next scheduled appointment and their success with cigarette tracking and study cigarette compliance.

Time commitment: 15 minutes

7.2.7 Remote visit 3 (scheduled for -1 to +1 day of in person MRI visit)

Participants will complete the following procedures over a Zoom call

1. Concomitant medications
2. Adverse event trigger questions
3. Perceived health risk rating
4. Computerized REDCap Survey Questionnaires (see Remote Visit 1)
5. Review cigarette tracking logs.
6. Complete computerized out-of-scanner tasks
7. Complete quit choice survey and counseling. Participants will be reminded that they will receive a text message survey in 12 weeks asking for information on quit attempts.

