1.0 Objectives

1.1 Study Objectives

The specific aims of the current study are to:

1) Examine the longitudinal effect of very low nicotine content (VLNC) cigarettes on changes in task-related functional neural activation within brain circuitry associated with incentive salience valuation and executive function. We hypothesize that, for the VLNC group compared to the normal nicotine content (NNC) group:

- a. Reactivity to smoking vs. pleasant odors within incentive salience circuitry will decrease.
- b. Reactivity to monetary rewards within incentive salience circuitry will increase.
- c. Activity during decision-making and inhibitory control within executive control circuitry will increase.

2) Assess the longitudinal effect of VLNC cigarettes on changes in effective (directional) connectivity between incentive salience and executive control brain circuitry. We hypothesize that, for the VLNC group compared to the NNC group:

- a. The influence of executive control over incentive salience circuitry, measured during task demands that simultaneously engage both processes, will increase.
- b. The influence of non-smoking reward salience circuitry over smoking salience circuitry during the odor cue reactivity task will increase.

3) Establish measurable and objective neural outcomes of successful reductions in smoking dependence.

1. We hypothesize that changes in functional activation and effective connectivity over the course of the VLNC intervention will be correlated with reductions in subjective and behavioral assessments of smoking dependence, including the number of cigarettes smoked per day, subjective reports of dependence, craving, and withdrawal.

4) Assess the effect of VLN Cigarettes vs NNC cigarettes on the levels of salivary miRNAs targeting dopamine, glutamate, acetylcholine and GABA-related transcripts over 6-weeks.

1. We hypothesize that the VLNC group will have significantly more changes in miRNA expression than the NNC group. A two-way repeated measures ANOVA will be conducted to compare changes in miRNA expression over three time points for the VLNC and NNC groups.

5) Determine if within-subject changes in miRNA expression are associated with changes in fMRI BOLD signal during smoking cue-reactivity and inhibitory control tasks for the VLNC group over 6-weeks.

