3.0 Inclusion and Exclusion Criteria

3.1 Inclusion Criteria

1. 21-60 years old
2. Smoke ≥5 cigarettes per day
3. >1 year of daily smoking
4. No quit attempt in prior month and not planning to quit smoking within next 3 months
5. Able to understand and consent to study procedures
6. Educational attainment < college degree or annual household income < \$50,000
7. Plan to live in local area next 3 months
8. Women not pregnant or nursing and not planning to become pregnant in the next 3 months
9. Able to read and write in English
10. Access to computer with internet service that allows for Zoom

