7.2.8 MRI visit 2 (Week 6 ± 5 days)

Participants will return to the CNMRR Center for their final MRI scan after refraining from smoking for 14 hours prior to the visit.

For the final study visit, participants will complete the following activities:

1. Return all (empty and full) cigarettes packs
2. Penn State CNMRR MRI safety and Scent Ratings (post MRI)
3. Urine collection for cotinine analysis and pregnancy determination: Obtain urine and process pregnancy test for women of child bearing age (have had a period in the past 12 months) who have not had a hysterectomy
4. Saliva collection for potential cotinine analysis, micro RNA (miRNA) biomarker analysis, and use in future research.
5. Exhaled carbon monoxide will be measured using a hand-held monitor.
6. Computerized REDCap Survey Questionnaires (nicotine withdrawal, smoking urges, craving)
7. The MRI technologist will first review the MRI safety sheet and determine that it is safe for the participant to be scanned. If safe, participants will complete a one-hour MRI scan.

Time commitment: 2 hours

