Aim 3: Establish measurable and objective neural outcomes of successful reductions in smoking dependence. FSL's Randomise one-sample t-test will be conducted on change scores to determine if changes in BOLD activity are associated with reductions in subjective markers of dependence (FTND, HONC, MNWS, QSU), cigarettes smoked per day, and quit intention and success. Changes in connectivity estimates will be correlated with changes in subjective and behavioral outcomes.

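### Remote Visit 3 may deliver quit counselling up to a day before the final scan: a minor, cheaply avoidable addition to the pooled baseline-to-week-6 change

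*Combined protocol and SAP*

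**What the plan says.** The week-6 assessment is split between a Zoom call and an in-person scan. The heading of the Zoom call is "7.2.7 Remote visit 3 (scheduled for -1 to +1 day of in person MRI visit"), and the last of its seven items begins "Complete quit choice survey and counseling". The in-person visit, section 7.2.8, is introduced with "For the final study visit, participants will complete the following activities". Its list includes the scan and "Computerized REDCap Survey Questionnaires (nicotine withdrawal, smoking urges, craving").

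The baseline pair is arranged differently. The Zoom call there is headed "7.2.3 Remote visit 1 (scheduled for +1 to +3 day(s) of in person MRI visit"), so it always follows its scan, and its list contains no quit counselling.

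Two other sections bear on the intended timing. Section 11.0 (Risks) says that all participants receive cessation counselling when the study ends. Section 12.1 says that it is offered to those who complete the study. Neither says that it must follow the final scan.

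In section 8.3, Aim 1 includes paired t-tests of baseline against 6-week scans across groups, which I read as both arms pooled. Aim 3 relates change in brain activity to change in "subjective markers of dependence (FTND, HONC, MNWS, QSU") and in other measures.

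**The concern.** Counselling about quitting is a second intervention. If it comes the evening before the scan, the participant's response to tobacco odor, smoking pictures and craving questions at week 6 may partly reflect that conversation. Nothing similar precedes the baseline scan, so any such effect goes entirely into the change score.

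The measures at risk are those taken at MRI Visit 2: the scan tasks, and the withdrawal, urge and craving questionnaires. The scan supplies one part of the primary endpoint in section 1.2, change in neural reactivity to tobacco odor. The withdrawal and urge questionnaires (MNWS and QSU) are two of the four subjective markers named for Aim 3.

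The analysis with least protection is the pooled paired comparison, because randomisation does not remove a shift common to both arms. Section 8.3 includes no adjustment for whether counselling or the scan came first.

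**Working it through.** **1. Order of events as written**

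| | Zoom call relative to its scan | Quit counselling on the call | Counselling before the scan possible? |
|---|---|---|---|
| Baseline (7.2.2, 7.2.3) | +1 to +3 days | none listed | no |
| Week 6 (7.2.7 Remote visit 3, 7.2.8) | -1 to +1 day | item 7 | yes, by up to one day |

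The possible exposure is one-sided.

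**2. Size in the pooled paired test**

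The plan gives no figure to reproduce on this point, and the sample-size figures in section 8.2 do not enter. Two inputs are needed that the documents do not give, so both are assumed:

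- s = share of participants counselled before the scan.
- d = shift caused by counselling, in SDs of the change score.

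From section 8.2, n = 75 completers, or 60 at 80% retention. The calculation is for one region or one symptom score, with no cigarette, time or repeat-scan effect, tested two-sided at 5%.

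- Mean shift = s × d.
- SD of change = √(1 + s(1−s)d²).
- Noncentrality = s × d × √n / SD, referred to the noncentral t with n−1 degrees of freedom.

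For example, at s = 0.5, d = 0.2 and n = 75, the mean shift is 0.100, the SD is √1.01 = 1.005, and the noncentrality is 0.100 × 8.660 / 1.005 = 0.862. The critical value is 1.993 and rejection is 13.6%.

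| s | d | mean shift (SD) | n = 75 | n = 60 |
|---|---|---|---|---|
| 0 | any | 0 | 5.0% | 5.0% |
| 0.1 | 0.1 | 0.010 | 5.1% | 5.1% |
| 0.25 | 0.2 | 0.050 | 7.1% | 6.7% |
| 0.5 | 0.2 | 0.100 | 13.6% | 11.8% |
| 1.0 | 0.2 | 0.200 | 40% | 33% |

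At n = 75, rejection reaches 10% when s × d is about 0.076 SD. The first row applies if staff always scan first. The last applies if Remote Visit 3 always comes first. The documents exclude neither.

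**3. The arm contrast**

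If s and d are the same in both arms, the shift cancels in expectation. With 50 and 25 participants the standard error of the difference is √(1/50 + 1/25) = 0.245 SD. If the share counselled first differs between arms by 20 percentage points, the bias is 0.2 × d. The two-sided test then rejects 5.1% to 5.7% of the time for d = 0.1 to 0.3. A 40-point difference gives 5.3% to 7.7%.

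**4. Added noise and induced correlation**

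Mixed ordering multiplies the standard error by √(1 + s(1−s)d²). If counselling shifts two change scores by the same d, it induces a correlation of s(1−s)d² / (1 + s(1−s)d²).

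| s | d | SE increase | induced correlation |
|---|---|---|---|
| 0.5 | 0.2 | 0.5% | 0.010 |
| 0.5 | 0.3 | 1.1% | 0.022 |
| 0.5 | 0.5 | 3.1% | 0.059 |

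These are values at assumed points. Since d is not bounded by anything in the documents, no ceiling can be given.

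**The case against.** The best reply is that the protocol already states its intention: counselling belongs at the end of the study, and a participant without a week-6 scan has hardly completed it. On that reading only a loosely drawn visit window remains. Eligibility also requires "No quit attempt in prior month and not planning to quit smoking within next 3 months", so one session may do little. The pooled change already mixes in time, repeat scanning and study contact, and would not be attributable to VLNC cigarettes even with perfect ordering. No planned conclusion is shown to change.

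Most of this stands, and it is why the point is minor. It does not remove the point: a statement of intent does not fix the order, and the window allows the opposite.

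A reader might infer more than the documents support:

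- **That the arm comparison is biased.** The Aim 1 and Aim 2 hypotheses are introduced with "We hypothesize that, for the VLNC group compared to the normal nicotine content (NNC) group", and counselling is for both arms. Bias would need a difference between arms in the share counselled first or in the effect of counselling. The documents indicate neither, though they do not rule them out.
- **That the paired test has an inflated type I error.** It remains a valid test of zero mean change. The rejection rates above describe a real change with a different cause, for one measure. They are not whole-brain rates.
- **That the dependence questionnaires are contaminated too.** The Remote Visit 3 questionnaires, log review and tasks are listed before item 7 and are unaffected if that order is followed. This is conditional, since list order is not always running order here: section 7.2.8 lists the post-scan scent ratings before the scan.

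**Conclusion.** The point holds as a minor one. The schedule permits, but does not require, quit counselling up to a day before the week-6 scan and its questionnaires, with no counterpart at baseline. This could add one avoidable component to the pooled within-person change from baseline to week 6.

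Its size is unknown and may be near zero. The 5.1%, 13.6% and 40% rejection rates at n=75 rest wholly on assumed shares and shifts. They show how the result depends on those inputs and do not estimate what this trial will see. The VLNC-versus-NNC contrast is unbiased on average provided that the share counselled first and the effect of counselling are equal in both arms. The effects on precision and on the Aim 3 correlations are small at the values tried, but cannot be bounded.

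Correcting the order removes this one source. It does not turn an uncontrolled change into an effect of VLNC cigarettes.

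**What to change.** State that the quit choice survey and counselling are given only after the MRI Visit 2 scan, scent ratings and withdrawal, urge and craving questionnaires are complete. Either of two arrangements does this:

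- **Move the visit.** Schedule Remote Visit 3 from after the scan to +1 day. This keeps the call whole, at the price of a slightly narrower scheduling window.
- **Split off item 7.** Keep the -1 to +1 day window for items 1 to 6 and give item 7 after the scan: at the end of MRI Visit 2 if the call came first, otherwise on the call. This lengthens a visit listed at 2 hours that follows 14 hours without smoking. It also needs someone at the scan site who can counsel, which the documents do not confirm.

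The first is simpler. Either takes one sentence of schedule wording, adds no contact, keeps the promise of counselling to all participants, and leaves the sample size and analyses unchanged. If staff already scan first, the sentence only records practice.
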